Thyroid hormones, thyroxine (T4) and triiodothyronine (T3), are produced in the follicular cells of the thyroid gland and can impact nearly every cell in the human body. They are essential to the human metabolism, influence the basal metabolic rate, bone growth, neural maturation, the body's sensitivity to catecholamines, cell development and differentiation as well as protein, fat and carbohydrate metabolism. With about 5000 µg, the thyroid is the largest storage of T4.^{1(p303)} Therefore, the maintenance of adequate thyroid hormones levels is crucial for the patient's quality of life after a hemithyroidectomy. The thyroid is constituted of a right and a left lobe as well as a connecting isthmus. In most patients, the right lobe is significantly larger than left lobe.² In a 2009 study by Ying and Yung, the right lobe was 6.8ml as opposed to the left lobe with a volume of 5.66ml.³ Although the remaining lobe adapts and continues to grow up to 30% from its original size to compensate for the loss,⁴, thyroid hormone supplementation is required in approximately 22% of all patients after thyroid lobectomy.^{5,6} In order to predict the necessity of thyroid hormone replacement therapy after hemithyroidectomy, risk factors such as a higher TSH before surgery, but also the resected thyroid volume have been identified in the past. Surprisingly, the resected thyroid volume showed significant negative correlation with postoperative TSH levels in a 2015 study by Lee et al.⁵ Previous studies aiming at optimizing post-surgery levothyroxine dosages incorporated sex, age, body surface area (BSA) and body mass index (BMI) but not if the right of left thyroid gland was resected into their calculations.^{7,8} Therefore, the study at hand aims at investigating a possible difference in levothyroxine requirements depending on the side of the resection to ensure adequate treatment.

2 Research questions and aims

- **Research Questions:** We hypothesize a possible influence of right vs left hemithyroidectomy on developing postoperative hypothyroidism as well as treatment dosage.
- **The aim** of this study is to be able to better predict the necessity, dosage and starting point of levothyroxine treatment after a hemithyroidectomy.

3 Study design

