4.2 Exclusion criteria

- Radiation therapy
- Pregnancy
- Previous thyroid surgery (e.g. nodule removal surgery)

Differences in Levothyroxine requirements after hemithyroidectomy

5 Primary and secondary parameters

The occurrence of post-surgery hypothyroidism and levothyroxine dosage is the primary outcome parameter. The secondary outcome parameter is the timespan between hemithyroidectomy and the need for levothyroxine treatment.

6 Methodology

The list of patients who underwent a hemithyroidectomy will be provided by the IT4Science department via a data extraction from the RDA database. Further information necessary for the analysis (side of hemithyroidectomy, type and dosage of treatment) will be extracted from the AKH-Informationsmanagement (AKIM) at the General Hospital of Vienna (AKH), analyzed and pseudonymized by [name] and, then, safely secured on a server at the Chiari Stoffwechsellambulanz.

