6.1 Statistical analysis

The collected data will be analyzed by descriptive statistics and illustrated in SPSS (Version 22) by using graphs, tables and boxplots. All data is password protected and anonymized to ensure adequate privacy protection.

Normally distributed data will be described by calculating median, mean and standard deviation. Patient baseline characteristics will be described as percentages and frequencies for categorical variables or mean and median values and standard deviation for normally distributed continual variables. In order to ensure comparability, a Levene's Test for Equal Variances will be performed. Differences of characteristics between the groups will be analyzed by unpaired T- tests for continuous variables. Possible confounding factors such as age, sex, underlying disease and BMI will be identified and adjusted for in a multiple logistic regression model.

In order to compare the levothyroxine dosages, a parametrical test (t-test) with a significance level of $p < 0.05$ will be performed. Adequate transformations such as the Levene's Test for Equal Variances will be applied to deal with not normally distributed residues and, thus, ensure comparable variances. For illustrational purposes, bar charts, histograms and boxplots will be used.

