6.1.2 Secondary hypothesis

H₀: There are no sex differences between men and women depending on the side of the resected thyroid lobe in the occurrence of hypothyroidism and the needed levothyroxine dosage after a hemithyroidectomy.

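### Section 6.1 describes Levene's test as a transformation; no real transformation, form of t-test or consequence of the Levene result is stated for the dosage comparison

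*Combined protocol and SAP*

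**What the plan says.** Section 5 makes dosage part of the primary outcome: "The occurrence of post-surgery hypothyroidism and levothyroxine dosage is the primary outcome parameter". The null hypothesis in section 6.1.1 also covers dosage.

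Section 6.1 gives the test: "In order to compare the levothyroxine dosages, a parametrical test (t-test) with a significance level of $p < 0.05$ will be performed". The next sentence is the only one on what to do if its assumptions fail: "Adequate transformations such as the Levene's Test for Equal Variances will be applied to deal with not normally distributed residues and, thus, ensure comparable variances".

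Levene's test also appears earlier in section 6.1: "In order to ensure comparability, a Levene's Test for Equal Variances will be performed". Unpaired t-tests for baseline characteristics follow, with no condition attached. No other section names a transformation, a threshold for Levene's test, an unequal-variance t-test or a rank-based alternative.

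**The concern.** Levene's test takes the data as they are and returns a statistic and a p-value for the hypothesis of equal variances. It is not a member of the class of methods that the sentence gives it as an example of. The sentence asks it to do two things it cannot do: deal with non-normal residuals, and bring variances into line.

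Once the wrong example is removed, three choices in a primary-outcome test are open:

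- whether the t-test assumes equal variances;
- what happens if Levene's test rejects;
- whether doses are transformed, and how.

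Each could be settled after the doses have been seen. The third also changes the quantity compared, since a difference in log dose is a ratio and not a difference in µg. That matters for a study whose stated aim in section 2 includes predicting dosage.

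**Working it through.** **Reading.** Each statement about Levene's test in section 6.1 can be set against what the test does.

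| Section 6.1 says it will | What the test does |
|---|---|
| ensure comparability (first mention) | reports evidence on equal variances; ensures nothing |
| serve as a transformation (second mention) | leaves every value unchanged |
| deal with non-normal residuals | does not assess or alter distributional shape |
| ensure comparable variances | tests for them; cannot produce them |

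A run on simulated skewed data confirmed this: it returned W = 11.15 and p = 0.001, and the data were unchanged.

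**Inputs from the documents.** Section 4 gives about 50 patients a year from 1994 to 2018: (2018 − 1994 + 1) × 50 = 25 × 50 = 1250, which reproduces the stated headcount. The background says that "thyroid hormone supplementation is required in approximately 22% of all patients after thyroid lobectomy", and 0.22 × 1250 = 275. This figure only sets a plausible number of patients with a dose; it does not define an analysis set.

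**Assumed inputs.** The documents give no dose SD, no left/right split and no sidedness. The SDs (µg) and splits below are assumptions, and the tests are taken as two-sided at 5%.

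**Formula for the equal-variance test.** With group sizes n1 and n2 and SDs s1 and s2:

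- true variance of the mean difference: V = s1²/n1 + s2²/n2
- variance the test uses, on average: P = [((n1−1)s1² + (n2−1)s2²)/(n1+n2−2)] × (1/n1 + 1/n2)
- large-sample type I error: 2 × [1 − Φ(1.96 × √(P/V))]

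**Worked case, 165 (SD 25) vs 110 (SD 30).** V = 625/165 + 900/110 = 3.788 + 8.182 = 11.970. P = [(164×625 + 109×900)/273] × (1/165 + 1/110) = 734.80 × 0.015152 = 11.133. √(P/V) = 0.9644, and 1.96 × 0.9644 = 1.890, so the type I error is 5.9%.

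**All cases.** The last three columns are simulated type I errors from normal data, 40,000 replicates per setting.

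| n1 (SD) vs n2 (SD) | V | P | √(P/V) | Formula | Equal-variance | Welch | Levene selects |
|---|---|---|---|---|---|---|---|
| 165 (25) vs 110 (30) | 11.970 | 11.133 | 0.9644 | 5.9% | 5.6% | 4.8% | 5.1% |
| 165 (30) vs 110 (25) | 11.136 | 11.973 | 1.0369 | 4.2% | 4.3% | 5.0% | 4.8% |
| 180 (25) vs 95 (40) | 20.314 | 15.450 | 0.8721 | 8.7% | 8.5% | 4.7% | 4.7% |
| 180 (40) vs 95 (25) | 15.468 | 20.332 | 1.1465 | 2.5% | 2.6% | 5.3% | 5.3% |
| 138 (25) vs 137 (40) | 16.208 | 16.156 | 0.9984 | 5.0% | 4.8% | 4.8% | 4.8% |

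In the first row, two further simulations gave 5.7% and 6.1% for the equal-variance test; the formula value lies between them. The error is above 5% when the smaller group has the larger SD, below 5% when the larger group does, and near 5% when group sizes are nearly equal.

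**Cost of Welch's test when SDs are equal.** For an assumed 10 µg difference and SD 30, simulated power was 76.5% (equal-variance) against 76.4% (Welch) at 165 vs 110, and 74.4% against 74.3% at 180 vs 95. A second run gave 77.2% against 77.1% and 74.8% against 74.7%.

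**The case against.** The strongest reply is that this is mainly a slip of wording in a study that section 3 calls exploratory. A familiar use of Levene's test is to choose between the equal- and unequal-variance versions of the t-test, and an analyst would probably do that. On that reading the error held at 4.6% to 5.3% over the settings simulated with normal data. It reached 5.5% to 5.8% when both shape and SD were made to differ by side, which is still small. The 8.7% figure needs an imbalance and an SD ratio that the documents do not give. All of this stands and limits the severity. It does not remove the point: the plan does not state that use, and that use would not address non-normality, which the sentence claims to handle.

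Three stronger readings are tempting, and the documents do not support them.

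- A reader might infer that the instruction cannot be carried out at all. The sentence prescribes suitable transformations and gives Levene's test as an example, so a real transformation could be applied under it. The fair charge is that none is named.
- A reader might infer that doses should be left untransformed, because Welch's test on skewed doses with the same distribution on both sides held its error at 4.8% to 5.3%. That is evidence on type I error only. With lognormal doses (mean 75, SD 45, skewness 2.0; 165 vs 110) and an assumed 18% higher dose on one side, power was 60% on raw doses and 68% on log doses. These compare different quantities, so they do not show that logging is right, but they do not let it be ruled out.
- A reader might infer from the phrase "the needed levothyroxine dosage after a hemithyroidectomy" in section 6.1.2 that only treated patients belong in the comparison. That phrase belongs to the secondary hypothesis on sex, and the primary null hypothesis does not exclude patients who need no dose. Which patients contribute a dose is a separate question that the Levene error does not settle.

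**Conclusion.** The point holds in limited form. Section 6.1 misdescribes a diagnostic test as a transformation and leaves the form of the t-test, the consequence of the Levene result and any transformation of dosage unstated. That follows from the text and needs no assumption.

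The numerical effect does rest on assumptions. It requires that the equal-variance test is always used and that both SDs and group sizes differ by side. Under the assumed inputs the type I error then runs from about 2.5% to 8.7%, and from about 4.2% to 5.9% in the milder case. A reader might infer that the primary dosage test is invalid or its false-positive rate materially inflated; the documents do not support that, because they give neither SDs nor the left/right split, nor do they say that the equal-variance test will be used. Nor does the plan say that doses are non-normal or unequal in variance; it only provides for that possibility.

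Severity is minor to should-fix. The case for acting is a wrong instruction in a primary-outcome test that is very cheap to correct.

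**What to change.** Replace the sentence with: *Levothyroxine dosages will be compared by side with Welch's unequal-variance t-test, whatever the result of Levene's test, which is descriptive only.* Reword the earlier mention in section 6.1 to match, so that Levene's test is reported and not said to ensure comparability.

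If a transformation for skewed doses is still wanted, name it (for example the logarithm) before the doses are seen, and state that the comparison is then of ratios and not of differences in µg.

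This settles only the unadjusted comparison that the plan names. It needs no new data and changes no stated figure. The cost is about 0.1 to 0.2 percentage points of power when the SDs are equal.

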6.1.1 Null hypothesis

H₀: The side of the resected thyroid lobe in a hemithyroidectomy does not influence the hypothyroidism occurrence and levothyroxine dosage requirements after surgery.

6.1.2 Secondary hypothesis

H₀: There are no sex differences between men and women depending on the side of the resected thyroid lobe in the occurrence of hypothyroidism and the needed levothyroxine dosage after a hemithyroidectomy.

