The study at hand is an exploratory retrospective study conducted on approximately 1250 patients who received a hemithyroidectomy at the Medical University of Vienna, Department of General Surgery, Division of Endocrine Surgery. A possible confounding factor is that the underlying conditions such as goiter or nodules which lead to the surgery might differ in the patients.

4 Patients

All patients who received a hemithyroidectomy at the Department of General Surgery, Division of Endocrine Surgery between 1994 and 2018 will be included in the study which are around 50 per year totalling around 1250 patients. Due to the study design, no power calculations have been conducted beforehand. However, considering similar studies^{5,6}, this sample size was deemed sufficient in order to achieve valid results and a statistical power of 0.8.

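### The secondary hypothesis (6.1.2) is a side-by-sex interaction for occurrence and dose, but section 6.1 contains no analysis that tests it

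*Combined protocol and SAP*

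**What the plan says.** Section 6.1.2 states a secondary null hypothesis in two parts. For occurrence: "There are no sex differences between men and women depending on the side of the resected thyroid lobe in the occurrence of hypothyroidism". For dose, in the same sentence: "and the needed levothyroxine dosage after a hemithyroidectomy".

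Section 6.1 is the only place where analyses are described. Sex appears there once, in a list of covariates: "Possible confounding factors such as age, sex, underlying disease and BMI will be identified and adjusted for in a multiple logistic regression model". The dose analysis is introduced with "In order to compare the levothyroxine dosages, a parametrical test (t-test) with a significance level of" 0.05, and no factor or covariate is attached to it. The remaining comparison is of group characteristics: "Differences of characteristics between the groups will be analyzed by unpaired T- tests for continuous variables". Section 6.1 mentions no interaction term, no sex-stratified or subgroup comparison, no two-way analysis of variance and no regression for dose.

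Section 4 says that no power calculation was done, yet adds that "this sample size was deemed sufficient in order to achieve valid results and a statistical power of 0.8". It ties that figure to no hypothesis, outcome or effect size.

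**The concern.** A sex difference that depends on which lobe was removed is, in model terms, a side-by-sex interaction. Adjusting for sex as a main effect estimates one common side effect. It cannot show whether that effect differs between men and women. A logistic model also cannot analyse a continuous dose, and the dose t-test does not involve sex. So the stated analyses cannot answer the stated hypothesis on either outcome.

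The direct consequence is that the test of a formal hypothesis would be chosen after the data are seen. A foreseeable fallback, which the document does not plan, is to compare sides separately in women and in men and to read significance in only one sex as a sex difference. When side has a real effect, that pattern is common without any sex difference, because power within each sex is limited and, if the sexes are unequal in number, also unequal.

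**Working it through.** **1. Hypothesis against analyses**

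| Part of 6.1.2 | Needed | Stated in 6.1 |
|---|---|---|
| Occurrence | Side × sex term in a logistic model | Logistic model with sex as a confounder; outcome not named; no interaction |
| Dose | Side × sex term in a linear model, or equivalent | t-test without sex |

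This comparison alone establishes the defect. The steps below only give its size.

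**2. The plan's own figures**

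Section 4 gives about 50 patients a year from 1994 to 2018: 50 × 25 = 1250, which agrees. The power of 0.8 cannot be reproduced, because no effect size, SD, side split or sex split is given.

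**3. Inputs**

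- From the documents: N = 1250 (section 4), and an average rate of 22% from the background text before section 2 ("thyroid hormone supplementation is required in approximately 22% of all patients after thyroid lobectomy"). That is a supplementation rate, used here as a proxy for hypothyroidism.
- Assumed: 625 patients per side; 50%, 70% or 80% women; the same rates and side split in both sexes; two-sided 5% tests.
- Also assumed, for dose: the same sex share among treated patients as overall, and a common SD.

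**4. A reference side effect**

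The side difference around 22% that gives power 0.80 is 25.3% against 18.7%. This is back-solved for illustration and is not a target set by the plan.

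- OR = (0.253/0.747)/(0.187/0.813) = 1.47, log OR ≈ 0.387
- SE = √[1/(625 × 0.253 × 0.747) + 1/(625 × 0.187 × 0.813)] = 0.138
- Power = Φ(0.387/0.138 − 1.96) ≈ 0.80

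**5. Precision of the interaction test for occurrence**

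With w the share of women, the SE is 0.138/√w in women and 0.138/√(1−w) in men. The interaction SE is therefore 0.138/√[w(1−w)]. Power is for a ratio of odds ratios of 1.47. The ratio detectable with 80% power is exp(2.80 × SE).

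| Women | Interaction SE | Power at ratio 1.47 | Ratio detectable at 80% power |
|---|---|---|---|
| 50% | 0.276 | 0.29 | 2.16 |
| 70% | 0.301 | 0.25 | 2.32 |
| 80% | 0.345 | 0.20 | 2.63 |

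The interaction SE is 2.0 to 2.5 times that of the side effect. A separate calculation on the risk-difference scale agrees: power for an interaction of 6.6 percentage points is 0.29, 0.25 and 0.20.

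**6. Precision for dose, if limited to treated patients**

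n = 0.22 × 1250 = 275. Interaction SE = √(4/n_women + 4/n_men) = 0.241, 0.263 and 0.302 SD. Multiplying by 2.80 gives detectable interactions of 0.68, 0.74 and 0.84 SD. For side itself, 2.80 × √(4/275) = 0.34 SD.

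**7. The within-sex fallback**

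Take the same odds ratio of 1.47 in both sexes, so that there is no interaction. The chance that exactly one sex is significant is p_w(1−p_m) + p_m(1−p_w), where p_w and p_m are the powers in women and men.

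| Women | Power, women / men | Exactly one significant |
|---|---|---|
| 50% | 0.51 / 0.51 | 0.50 |
| 70% | 0.65 / 0.34 | 0.55 |
| 80% | 0.71 / 0.24 | 0.61 |

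A simulation of 200,000 runs gave the same three values, with the interaction test rejecting in 5.0% each time.

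For other side effects, over the same range of women:

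- 24.3% against 19.7% (overall power 0.50): 0.41–0.44
- 26.2% against 17.8% (overall power 0.95): 0.40–0.61
- No side effect: 2 × 0.05 × 0.95 = 0.095

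**The case against.** The strongest objection is that 6.1.2 is peripheral. Section 3 calls the study exploratory, and sex appears neither in the research question and aim (section 2) nor among the outcome parameters (section 5). The proposed test would have power of only 0.20 to 0.29 for an interaction as large as the reference side effect. This stands as an argument about severity: the change should be made but is not critical. It does not supply the missing analysis. Low power is also a reason to fix in advance an interval estimate in place of a choice among p-values.

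The 50–61% figures describe an analysis that nobody has planned. That is correct. They illustrate a risk, and the defect does not rest on them. Nor is low power in both sexes always the cause: at 95% overall power with 80% women, power is about 0.90 in women and 0.36 in men, and the imbalance produces the 61%.

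The wording of 6.1.2 is loose and could mean sex differences within each side. On that reading too, section 6.1 states no analysis. The sponsor should still say which is meant.

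The side split and the 22% rate were each used at one value, and an interaction on the odds-ratio scale need not match one on the risk-difference scale. Both points limit the exactness of the figures but not the conclusion.

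**Conclusion.** The concern holds. Section 6.1.2 poses a formal hypothesis on two outcomes, and carrying out section 6.1 to the letter tests neither. This follows from the text and needs no assumption.

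The size does rest on the assumptions listed in the check. Under them, a properly specified interaction test would reliably detect only large differences: a ratio of odds ratios of about 2.2 to 2.6 for occurrence, or 0.68 to 0.84 SD for dose in treated patients. The misleading alternative would show one sex significant and the other not in about 40–61% of studies across the three side effects examined, with no sex difference present. The change should be made. The study's exploratory status keeps it below an essential correction.

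**What to change.** In section 6.1:

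- Confirm that 6.1.2 means a side-by-sex interaction.
- Add a side × sex term to the logistic model, naming hypothyroidism occurrence as its outcome, and test the occurrence part of 6.1.2 by that term.
- Add a linear model for dose with the same term, and state whether it covers treated patients only or all patients. Section 6.1 does not say which, and the precision depends on it.
- Report the side effect in each sex and the interaction estimate, all with 95% confidence intervals.
- State that a sex difference will not be inferred from separate within-sex p-values, and label the test exploratory.

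The cost is one term per model, a linear model for dose beside the t-test, and a few sentences. No new data should be needed, since sex is already a planned covariate. The drawback is that the test will rarely settle the question. Its value is a prespecified answer with an honest interval.

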6.1.3 Number of patients

Approximately 1250 patients

7 Data protection

Various measures will be implemented to ensure data protection and avoid unauthorized use and loss of data. Data will be stored on a secure server at the Medical University of Vienna, Chiari Stoffwechselambulanz which is password protected and kept in a locked room. Only authorized personnel have access to the Chiari Stoffwechselambulanz and the server. A full description of the technical and organizational measures can be provided on request. Data protection for this study is the responsibility of [name].

8 Benefit-risk assessment

Although there is no direct benefit for the patients due to the retrospective character of the study, negative side effects are not to be expected as well. Besides a possible data breach, which is minimized by pseudonymization and data protection, the patients are not at risk in any way. The results obtained in this study can be used to optimize patient care.

9 References

